3	5	8	40	72.00	60.00

Note – the first 6 evaluable patients enrolled will be treated at Dose Level 1 Please refer to section 10.0

Version 09/11/2025 page 10 of 63

SCHEDULE OF ACTIVITIES

	Screening	Pre- treatment ⁸	Radiation	1-2 Weeks post RT	6-8 Weeks post RT	3 Mo post RT ¹	6 Mo post RT ¹	9 Mo post RT ¹	12 Mo post RT ¹	
Informed consent	X^2									
H&P / PS / weight / DRE ¹³	X^2		X^3	X	X	X	X	X	X	
MRI pelvis ⁴	X^2				X	5	X	X	X	
CT chest / abdomen / pelvis with contrast ⁶	X^2				X ⁶		X	X	X	
Endoscopy ⁷	X^2				X	15				
OPTIONAL biopsy	$X^{2, 15}$				Х	ζ				
CBC w/diff	X^2	X^2			X^9		X			
CMP	X^2	\mathbf{X}^2			X^9		X			
CEA		X			X^9		X			
SCCA		X			X ⁹		X			
CRP		X			X ⁹		X			
LDH		X			X ⁹		X			
Pregnancy test	$X^{10,11}$									
Radiation therapy			X^{12}							
EORTC QLQ-C30		X		X		X	X	X	X	
EORTC QLQ-C29		X		X		X	X	X	X	
Adverse events		X	X^3	X	X	X	X	X	X	

- 1. +/- 2 weeks
- 2. No more than 60 days prior to registration. Screening and baseline labs can be the same draw provided the timing aligns.
- 3. Performed once during radiation therapy.
- 4. Cross-sectional imaging with either MRI or CT is acceptable.
- 5. MRI pelvis and CT chest/abdomen with contrast may be obtained 6 weeks to 3 months after radiation completion with a RECIST read at 3 months only.
- 6. If PET/CT scan is done, then CT chest/abdomen/pelvis not required.
- 7. Endoscopy with colonoscopy, sigmoidoscopy, or proctoscopy will be performed if feasible after screening.
- 8. Baseline labs and QOL assessments should be performed within 30 days of radiation therapy.
- 9. Labs should be drawn once 6 weeks to 3 months after radiation completion but should be drawn before surgery if the patient undergoes salvage surgery.
- 10. Mandatory for women of childbearing potential.
- 11. Within 14 days of registration.
- 12. 5 fractions over 1 week.
- 13. DRE only to be done if feasible.15. OPTIONAL endoscopy with biopsy performed 6 weeks to 3 months after completion of RT; for research purposes only.
- 15. OPTIONAL screening biopsy to be performed at time of baseline SOC endoscopy.

Version 09/11/2025 page 11 of 63

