1.2 Reirradiation

Given the clinical challenges and limitations with salvage surgery, investigators have explored pelvic reirradiation with and without salvage surgery and chemotherapy in the setting of LRRC (22–24). Reirradiation of the pelvis poses significant risks due to the cumulative effects on the organs at risk (OARs), such as the residual rectum, bladder, small, and large bowel, and the maximum lifetime dose to OARs for which toxicities outweigh the benefits of local-regional control remain undefined (25). Studies have reported reirradiation using conventional fractionation (1.8-2.0 Gy/fraction daily) (26–32) and hyperfractionation (1.2-1.5 Gy/fraction twice a day) (26, 33–37).

Version 09/11/2025 page 12 of 63

Metanalyses of these reirradiation studies showed pooled 1-, 2-, and 3-year OS rates for patients who received reirradiation and surgery were 86%, 72%, and 52%, respectively (24). The pooled grade ≥3 acute and late complication rate was 12% in patients who underwent reirradiation alone and was 26% in patients who underwent reirradiation and surgery (24). However, the 3-year OS was merely 24% in patients who received reirradiation alone (24). Since the low doses of 30-45 Gy delivered via conventional or accelerated hyperfractionation with photon therapy are generally insufficient to eradicate gross disease and are considered to the be palliative without salvage surgery (24).

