5.4 Definitions of Evaluability

Endpoint	In order to be evaluable for this endpoint, a		
	patient must		
	Have received at least one fraction of study		
	radiation. Patients will be evaluated for DLTs		
Maximum tolerated dose	from the start of treatment through 6 months		
	after the start of treatment. DLT is defined in		
	Section 5.2.1.		
Clinical complete response rate.	Have received at least one fraction of study		
	radiation and undergone response assessment by		
	DRE, endoscopy, and/or cross-sectional		
	imaging.		
Freedom from locoregional	Have received at least one fraction of study		
progression (FFLP) at 12 months.	radiation and undergone response assessment.		
Overall survival at 12 months.	Have received at least one fraction of study		
	radiation		
Progression-free survival at 12	Have received at least one fraction of study		
months.	radiation and undergone response assessment.		

Version 09/11/2025 page 27 of 63

Patient reported quality of life.	Have completed the EORTC QLQ-C30 and/or QLQ-CR29 QOLs at pre-treatment and a minimum of one post-treatment time point
Toxicity	Have received at least one fraction of study radiation. Patients are evaluated from first receiving study radiation until 12 months after the conclusion of radiation.
Association of pre-treatment SCCA and post-treatment SCCA with PFS and OS at 6 months.	Have had blood drawn for SCCA at screening and after completion of study radiation
Levels of serum inflammatory markers.	Have had blood drawn for CRP and LDH after completion of study radiation

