10.2 Simulation and Sample Size Calculations

The TITE-CRM manual details methods for utilizing trial simulation in order to obtain estimated posterior probabilities on toxicity estimates. We utilized the simulation program to determine the efficacy of our trial and obtain estimates for needed sample size. While there is no exact power calculation for this type of trial, the effectiveness of the trial's sample size can be determined by looking at the stability of the posterior probability under different prior probabilities.

We ran 1000 simulations under various increasing and decreasing prior probability estimates utilizing the previously described rules and assumptions for this trial and saw sufficient stability in posterior probability estimates with a sample size of 20 patients with a run-in of 6 patients. Simulations showed that approximately 95% of the time the trial will come to completion and the MTD will fall between the 3rd and 5th dose level 89% of the time. Therefore, we will use a fixed sample size of 20 patients for this trial. The posterior probability distribution of these 1000 simulations follow in the next table.

Version 09/11/2025 page 41 of 63

Dose Level	Estimated	Mean
	initial	Posterior
	toxicity	toxicity (SD)
d-1	0.25	0.328 (0.434)
1	0.30	0.38 (0.453)
(Starting		
Dose)		
2	0.35	0.43 (0.463)
3	0.40	0.479 (0.464)

Summary of simulation with estimated posterior probabilities. SD, Standard Deviation

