10.2.5 Analysis Plan

The primary endpoint of the study is to determine the maximum tolerated dose (MTD) of reirradiation using hypofractionated IMPT for patients with locoregionally recurrent rectal cancer. The MTD will be defined as the dose associated with a 35% probability of dose-limiting toxicity (DLT) as described above.

The secondary endpoints are clinical complete response rate, freedom from locoregional progression (FFLP), overall survival (OS), progression-free survival (PFS), PRO QOL, and adverse events as defined by CTCAE version 5.

Descriptive statistics will be calculated on all variables. Frequencies will be computed for all binary/categorical variables, and continuous variables will be summarized using medians, quartiles, and ranges. Next all variables will be compared with the historical data using Chi-square tests for binary/categorical variables and t-tests for continuous variables.

All the survival events will be measured from the end of radiation therapy and subjects who do not develop events will be censored at the last follow-up. Patients with distant metastasis will be continued to be followed for locoregional tumor recurrence until the last follow-up or time of death whether. Death will be analyzed as a competing cause in FFLP. Kaplan-Meier curves will be performed to compare the freedom from locoregional progression (FFLP), progression-free survival (PFS) and overall survival (OS). Cox proportional hazard model with log-rank test will be used to explain the correlation between explanatory variables and survival times.

Version 09/11/2025 page 43 of 63

Adjusted hazard ratios (HR) and the corresponding 95% confidence intervals (CI) will be reported.

PRO QOL questionnaires (Appendix B and C) will be tabulated for each domain and summed to generate a composite global QOL score. Repeated measures ANOVA will be used to compare QOL scores collected at baseline and at 1-2 weeks, 3 months, 6 months, 9 months, and 12 months after RT.

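### The six-visit repeated measures ANOVA for QOL has no rule for missing forms or death; fitted classically, it would drop patients whom section 5.4 counts as evaluable

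*Combined protocol and SAP*

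**What the plan says.** Section 10.2.5 gives the comparative QOL analysis in one sentence. It opens "Repeated measures ANOVA will be used to compare QOL scores collected at baseline", and its list of visits reads "QOL scores collected at baseline and at 1-2 weeks, 3 months, 6 months, 9 months, and 12 months after RT". That makes six assessments per patient.

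The section names no procedure, covariance structure or rule for a missing form, and does not say how death enters the QOL analysis. For the survival endpoints it does set rules: censoring at last follow-up, and death as a competing cause for locoregional progression. Software is R or SAS.

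Section 5.4 defines who is evaluable for QOL: "Have completed the EORTC QLQ-C30 and/or QLQ-CR29 QOLs at pre-treatment and a minimum of one post-treatment time point". Section 5.8 ends follow-up at 12 months or death. Section 10.2 sets the size of the trial: "Therefore, we will use a fixed sample size of 20 patients for this trial". That number comes from the dose-finding simulations, not from a QOL calculation.

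**The concern.** Classical repeated measures ANOVA needs a full row of scores for each patient. Someone with a baseline form and one to four later forms is evaluable under section 5.4 but would not enter the fit. The 12-month form can come only from a patient alive at 12 months, so complete cases are survivors by construction.

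QOL is a named secondary objective, and section 2 justifies it by the scarcity of such data in these patients. A trajectory from a selected subset could be read as the experience of everyone treated, and it would be less precise than the data allow. The monitoring table in Appendix F reports the number evaluable for each objective, so it could show a count well above the number that supplies the comparison.

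**Working it through.** The plan gives no expected number of complete QOL cases, so there is no figure to reproduce. The check compares the patients a classical fit would keep with those section 5.4 would count.

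**Inputs**
- Patients: 20 (section 10.2).
- Assessments: 6 (section 10.2.5).
- Upper 12-month survival, 86% (section 1.2): "pooled 1-, 2-, and 3-year OS rates for patients who received reirradiation and surgery were 86%, 72%, and 52%, respectively".
- Lower 12-month survival, derived (section 1.2): "the 3-year OS was merely 24% in patients who received reirradiation alone". No 1-year figure is given for that group. A constant hazard (assumption) gives 0.24^(1/3) = 0.621, or 62%.
- Salvage surgery is possible on study. A Schedule of Activities footnote says that labs "should be drawn before surgery if the patient undergoes salvage surgery". The share having surgery is not given, so both survival values are carried.
- Completion per form among living patients, c: not given. Assumed 90-95%, with 80-100% as the wider range, independent between visits.

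**Step 1: deaths alone (c = 100%)**
- 86%: 20 × 0.86 = 17.2 alive, 2.8 lost.
- 62%: 20 × 0.621 = 12.4 alive, 7.6 lost.

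So about 3 to 8 of 20 are lost with perfect compliance.

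**Step 2: patients with all six forms = 20 × S(12) × c^6**

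| c | S(12) = 62% | S(12) = 86% |
|---|---|---|
| 100% | 12.4 | 17.2 |
| 95% | 9.1 | 12.6 |
| 90% | 6.6 | 9.1 |
| 80% | 3.3 | 4.5 |

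At 90-95% completion this is about 7 to 13 of 20; over the whole grid, about 3 to 17. Treating the baseline form as always present (c^5) gives 7.3 to 13.3 at 90-95%, which is the same after rounding.

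**Step 3: patients evaluable under section 5.4 = 20 × c × P(at least one later form)**

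Take visits at t = 1.5/52, 0.25, 0.5, 0.75 and 1 year, and survival S(t) = S(12)^t. Then P(no later form) = 1 − S(t1) + Σ [S(tk) − S(tk+1)] × (1 − c)^k for k = 1 to 5, with S(t6) set to 0.
- 62% survival, c = 90%: P(no later form) = 0.0246, so 20 × 0.9 × 0.9754 = 17.6. At c = 95%: 18.6.
- 86% survival: 17.9 at c = 90% and 18.9 at c = 95%.

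About 18 to 19 are evaluable. At 80% completion the figure is 15.4 to 15.8.

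**Step 4: behaviour of the fits**

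One 20-patient data set was simulated with 62% survival and 90% completion. Seven patients had all six forms. A standard repeated measures ANOVA routine rejected the data as unbalanced; a mixed model used all 90 forms from all 20 patients.

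**The case against.** The strongest reply is that the plan never says incomplete patients will be deleted. The name is sometimes also used for mixed-model fits that keep partial data, and R and SAS offer both. This stands: deletion is the usual behaviour of the classical fit, not a stated rule. But the same sentence then permits two quite different analysis sets, which is a reason to specify.

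Second, the counts rest on borrowed survival and assumed completion. The 24% figure comes from reirradiation without surgery, while this trial escalates dose and allows salvage surgery. Missed forms may also cluster in the same patients. With full clustering at 90%, 20 × 0.621 × 0.9 = 11.2 to 20 × 0.86 × 0.9 = 15.5 would remain. This also stands, so the counts are illustrations. The mismatch with section 5.4 does not depend on them.

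Third, the ANOVA is not the only QOL output. Descriptive summaries and tabulation by domain are also planned, and patients with partial data can contribute there. That is correct; the point concerns the comparison over time.

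Four stronger readings are tempting but not supported:
- A reader might infer that half or more of the sample must be lost. At 86% survival and 95% completion, 20 − 12.6 = 7.4 are lost, or 37%.
- A reader might infer that those lost are mainly deaths. At 90% completion, deaths make up 7.6 of 13.4 losses (57%) at 62% survival but only 2.8 of 10.9 (26%) at 86%.
- A reader might put the bias at a set number of QOL points. That needs the QOL difference between complete and incomplete patients, which the documents do not give.
- A reader might take unequal visit spacing as a breach of sphericity. Spacing alone does not imply that.

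**Conclusion.** The point holds as a mismatch between the named method and the evaluability rule, with no provision for missing forms or death. Fitted classically, the analysis would describe 12-month survivors with full compliance and lose precision. The most secure figure is the loss from death alone, about 3 to 8 of 20, which rests on 12-month survival of 86% to 62%; the lower value assumes a constant hazard. The figure of about 7 to 13 complete cases against about 18 to 19 evaluable further assumes 90-95% independent completion. A survivor-only trajectory could well look too favourable, but the documents do not allow that to be sized. Only a secondary endpoint is affected; dose assignment, the stopping rule and the MTD do not use QOL. This is a cheap improvement.

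**What to change.** In section 10.2.5, replace the ANOVA with a linear mixed model for each QOL scale: visit as a categorical effect, a parsimonious within-patient covariance suited to 20 patients, a small-sample degrees-of-freedom correction, and all observed forms used. This brings in the patients whom section 5.4 counts as evaluable. Report the number alive and the number of forms received at each visit.

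State two limits. The estimates assume missing at random. The model does not define QOL after death, so results should be interpreted while patients are alive; without that statement, the fitted means implicitly carry scores past death.

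The cost is a few sentences of analysis text, with the same data and software and no added patient burden. The downside is small: a covariance form must be chosen in advance, and missing at random cannot be verified from the data.

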5.8 Duration of Follow-up

Patients will be followed for 12 months following the completion of IMPT or until death, whichever occurs first. Patients removed from study for unacceptable adverse events will be followed until resolution or stabilization of the adverse event. Follow-up is described in Section 5.3.4. Patients will be followed by office visits, phone calls, and review of medical record. Any additional follow-up and imaging will be obtained off-study as per routine clinical policies of the treating physician.

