5.9 Lost to Follow-Up

A participant will be considered lost to follow-up if he or she fails to return for 3 scheduled visits and is unable to be contacted by the study team.

The following actions must be taken if the participant fails to return to clinic for a required study visit:

- The study team will attempt to contact the participant and reschedule the missed visit within 5 business days and counsel the participant on the importance of maintaining the assigned visit schedule and ascertain if the participant wishes to and/or should continue in the study.
- O Before a participant is deemed lost to follow-up, the investigator or designee will make every effort to regain contact with the participant (where possible, 3 telephone calls and, if necessary, a certified letter to the participant's last known mailing address). These contact attempts should be documented in the participant's medical record or study file.

Version 09/11/2025 page 29 of 63

• Should the participant continue to be unreachable, he or she will be considered to have withdrawn from the study with a primary reason of lost to follow-up.

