Adverse events or treatment-related toxicities will be classified as acute (<3 months after RT completion) toxicities and late (3-12 months after RT completion) toxicities. Adverse events, along with their maximum grade and relationship to study treatment, will be tabulated and assessed descriptively for patterns of occurrence. Frequency tables will include frequencies and percentages at the patient level as well as at the AE level. Point estimates for proportions will be reported, along with small sample confidence interval estimates.

All analyses will be performed in R (RFoundation for Statistical Computing) or in SAS (SAS Institute, Inc.; Cary, NC).

Version 09/11/2025 page 44 of 63

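### Late toxicity (3-12 months) is in effect planned as a crude proportion of all treated patients, so patients lost before month 12 count as fully observed non-events

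*Combined protocol and SAP*

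**What the plan says.** Section 10.2.5 splits toxicity into an acute period (under 3 months) and "late (3-12 months after RT completion) toxicities". On presentation it says: "Frequency tables will include frequencies and percentages at the patient level as well as at the AE level". On estimation: "Point estimates for proportions will be reported, along with small sample confidence interval estimates". It gives no denominator for the late window.

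The only evaluability rule for toxicity is in Section 5.4. A patient enters with a single study fraction, and the observation period is: "Patients are evaluated from first receiving study radiation until 12 months after the conclusion of radiation". Nothing requires the patient to be alive or in follow-up at month 3.

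The plan expects some patients not to be observed throughout. Section 5.8: "Patients will be followed for 12 months following the completion of IMPT or until death, whichever occurs first". Under Section 5.9, an unreachable participant is "considered to have withdrawn from the study with a primary reason of lost to follow-up". Section 10.2.3 replaces patients who withdraw without a DLT for reasons other than toxicity, but Section 5.4 keeps them evaluable for toxicity.

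Elsewhere the plan does allow for incomplete observation. Section 10.2.5 treats death as a competing event for freedom from locoregional progression (FFLP) and censors the survival endpoints. Section 10.2.1 weights DLT-free patients by time observed.

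**The concern.** A late event can be recorded only in a patient who is alive and under observation after month 3. If the denominator is everyone treated, a patient lost at month 4 contributes the same as one followed without an event to month 12. The confidence interval likewise treats the missing months as observed.

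The toxicity profile is a secondary objective, and Section 2 justifies it on the ground that the profile of this regimen is not known. DLT observation ends 6 months from the start of treatment, so the late-toxicity table is the main summary of what happens after that. Section 10.2.5 also plans to compare all variables with historical data, so the percentage may be set beside series with different follow-up. The distortion runs towards apparent safety.

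**Working it through.** The plan states no late toxicity rate, dropout rate or precision target, so there is no figure of its own to reproduce. The following is an illustration.

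**Inputs from the documents**
- Section 1.2: 3-year OS 24% with reirradiation alone; 1-year OS 86% with reirradiation plus surgery.
- Section 10.2: "we will use a fixed sample size of 20 patients for this trial".

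**Assumptions**
- Late toxicity risk over months 3-12 of 20% in a patient observed throughout (10% and 30% as a range).
- Dropout of 0%, 10% or 20% by month 12.
- Constant hazards.

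**Step 1. Yearly hazards**
- Death: h = -ln(0.24)/3 = 0.4757, or h = -ln(0.86) = 0.1508.
- Late toxicity: l = -ln(0.80)/0.75 = 0.2975.
- Dropout: c = -ln(0.90) = 0.1054, or -ln(0.80) = 0.2231.

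**Step 2. Alive at month 3**
exp(-0.25h) = 0.888 or 0.963. Of 20 patients, about 2.2 or 0.7 have died by then.

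**Step 3. Three summaries**
- Crude proportion of all treated: exp(-0.25(h+c)) × l/(l+h+c) × [1 - exp(-0.75(l+h+c))].
- Cumulative incidence from RT (death competing, losses censored): the same expression with c = 0.
- Cumulative incidence from month 3: the second divided by exp(-0.25h).

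For h = 0.4757 and no dropout: 0.888 × (0.2975/0.7732) × [1 - exp(-0.5799)] = 0.150. Dividing by 0.888 gives 0.169.

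| Survival figure used | Assumed dropout | Crude, all treated | Cumulative incidence from RT | Crude ÷ incidence from RT | Cumulative incidence from month 3 |
|---|---|---|---|---|---|
| 3-year OS 24% | 0% | 15.0% | 15.0% | 1.00 | 16.9% |
| 3-year OS 24% | 10% | 14.1% | 15.0% | 0.94 | 16.9% |
| 3-year OS 24% | 20% | 13.2% | 15.0% | 0.88 | 16.9% |
| 1-year OS 86% | 0% | 18.2% | 18.2% | 1.00 | 19.0% |
| 1-year OS 86% | 10% | 17.1% | 18.2% | 0.94 | 19.0% |
| 1-year OS 86% | 20% | 16.0% | 18.2% | 0.87 | 19.0% |

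Ratios are taken before rounding. They hardly change with the assumed risk. With 3-year OS of 24% and no dropout, a 10% risk gives 7.5% crude against 8.4% from month 3, and a 30% risk gives 22.6% against 25.5%.

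**Step 4. Reading the table**
With no dropout, the crude figure equals the cumulative incidence from RT, so deaths alone do not bias it for that quantity. They lower it only relative to the risk among patients who reach month 3. Dropout lowers it relative to both.

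**Step 5. Against the precision available**
Clopper-Pearson 95% intervals for three late events:
- 3/20 = 15.0% (3.2% to 37.9%)
- 3/18 = 16.7% (3.6% to 41.4%)
- 3/16 = 18.8% (4.0% to 45.6%)

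**The case against.** **Deaths are a matter of estimand.** The share of treated patients who develop late toxicity is a legitimate quantity, and with complete follow-up the crude percentage estimates it correctly. This stands. A reader might infer from the working that the plan would report 15.0% where the truth is 20%. The documents do not support that: they give no late toxicity rate, and the 20% is an assumed risk in patients observed throughout, as if nobody died. Cumulative incidence with death competing does not estimate it either.

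**The denominator is inferred.** Section 10.2.5 does not say that all treated patients form the late-window denominator, and the toxicity row in Section 5.4 does not address the acute/late split. This stands too. But Section 5.4 is the only rule available, and if another denominator is meant, the plan does not give it.

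**The survival extrapolation may be pessimistic.** Applied to the 52% 3-year OS with surgery, a constant hazard gives 0.52^(1/3) = 80% at 1 year, whereas Section 1.2 gives 86%. The early deaths derived from the 24% figure may therefore be too many.

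**Loss may be small.** Patients who stop treatment early are still followed (Section 5.7). Telehealth visits, phone calls, record review and community sites are allowed (Sections 5.3.4, 5.8 and 4.6), and loss requires three missed visits and failed contact (Section 5.9). These steps reduce the number lost but do not say how those patients are analysed.

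**No decision depends on it.** Toxicity is tabulated descriptively, and dose assignment, the MTD and the stopping rule use time-weighted DLT data. This is correct and limits the weight of the point.

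**Conclusion.** The point holds in a limited form, as a cheap improvement. The two sections together imply a crude proportion of all treated patients, without censoring or number at risk.

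- **Losses and withdrawals** understate late toxicity under either estimand, by a factor of about 0.94 at 10% dropout and 0.88 at 20%. Both dropout rates are assumptions. Replaced withdrawals stay in the denominator and add to the effect.
- **Deaths** dilute the figure only as the risk among patients who reach month 3: by about 2 points using the reirradiation-alone survival and under 1 point using the surgery survival. This assumes a 20% late risk and constant hazards.

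Both shifts are small beside an interval running from 3.2% to 37.9%, but they go in one direction and a wide interval does not remove them. It should not be inferred that the dose-finding result is affected.

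**What to change.** In Section 10.2.5:

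1. Report late toxicity as the cumulative incidence to 12 months after RT among patients alive and in follow-up at 3 months after RT, with death as a competing event and loss to follow-up or withdrawal as censoring.
2. Show the number at risk at month 3.
3. Keep the crude late-event counts as a listing.
4. Keep all treated patients as the denominator for acute toxicity.

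This matches the handling of death already planned for FFLP. The toxicity, follow-up and death forms in Section 7 should supply the data, and the acute/late split already needs event dates. Censoring assumes that patients who leave have the same later risk as those who stay, which the SAP should say.

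The cost is a few lines of SAP text and one extra table, with slightly wider intervals and a slightly higher stated rate. Treatment, visits and sample size do not change.
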